## 6.2 DATA SHARING PLANS

### 6.2.1 Human Data Sharing Plan

**I will share human data generated in this research for future research as follows:**

Coded, linked data in an NIH-funded or approved public repository.

Coded, linked data in BTRIS (automatic for activities in the Clinical Center)

Coded, linked or identified data with approved outside collaborators under appropriate agreements.

**How and where will the data be shared?**

Data will be shared through:

An NIH-funded or approved public repository. Insert name or names: ClinicalTrials.gov, dbGaP.

BTRIS (automatic for activities in the Clinical Center)

Publications and/or public presentations.

**When will the data be shared?**

At the time of publication or shortly thereafter.

## 6.2.2 Genomic Data Sharing Plan

This study will comply with the NIH Genomic Data Sharing Policy, which applies to all NIH-funded research that generates large-scale human or non-human genomic data, as well as the use of these data for subsequent research. Large-scale data include genome-wide association studies (GWAS), single nucleotide polymorphisms (SNP) arrays, and genome sequence, transcriptomic, epigenomic, and gene expression data.

Therefore, unlinked genomic data will be deposited in public genomic databases such as dbGaP in compliance with the NIH Genomic Data Sharing Policy.

## 6.3 RESPONSE CRITERIA

Although response is not the primary endpoint of this trial, participants with measurable disease will be assessed by standard criteria. For the purposes of this study, participants should be re-evaluated as outlined in [Appendix D: Study Calendar](#)

. In addition to a baseline scan, restaging scans will be performed after cycles 1, 3, and 6. Cases with complete resection of tumor mass will not be evaluable for response assessment; however, will be included in the PFS and OS statistics. When appropriate, for participants with disease involvement of the bone marrow at baseline, repeat assessment will be done to confirm response.

### 6.3.1 Response Criteria for PCNSL

The following response criteria as per the CNS lymphoma working group ([\[35\]](#)) will be used for participants on study with PCNSL:

Response	Brain Imaging	Corticosteroid dose	Eye examination	CSF cytology
CR	No contrast enhancement	None	Normal	Negative
CRu	No contrast enhancement	Any	Normal	Negative
	Minimal abnormality	Any	Minor RPE abnormality	Negative
PR	50% decrease in enhancing tumor	Irrelevant	Minor RPE abnormality or normal	Negative
	No contrast enhancement	Irrelevant	Decrease in vitreous cells or retinal infiltrate	Persistent or suspicious
PD	25% increase in lesion	Irrelevant	Recurrent or new ocular disease	Recurrent or positive
	Any new site of disease: CNS or systemic			

Abbreviations: CR, complete response; CRu, unconfirmed complete response; RPE, retinal pigment epithelium; PR, partial response; PD, progressive disease

### 6.3.2 Response Criteria for SCNSL

The response categories being used to assess overall efficacy of combination therapy are based on the Revised Response Criteria for Malignant Lymphoma [\[36\]](#).

### 6.3.2 Complete Response (CR)

For CR determination, all the following criteria must be met:

1. Complete disappearance of all detectable evidence of disease and disease-related symptoms, if present before therapy
2. All lymph nodes and nodal masses must have regressed on CT to normal size ( $\leq 1.5$  cm in the greatest transverse diameter [GTD] for nodes  $> 1.5$  cm before therapy, regardless of the short axis). Previously involved nodes that were between 1.1 cm and 1.5 cm in the long axis and more than 1.0 cm in the short axis before treatment must have decreased to  $\leq 1.0$  cm in the short axis after treatment. All splenic and hepatic nodules and other extranodal disease must have disappeared.
3. FDG-PET scan must be negative (for the combined CT+PET assessment of CR). A posttreatment residual mass of any size is permitted as long as it is PET-negative. The Five-Point Scale (5-PS) Deauville criteria will be used to interpret PET scans with a score of 1-3 being considered PET negative and 4-5 considered PET positive [37] (Section 6.3.6).
4. The spleen and/or liver, if enlarged before therapy on the basis of physical examination or CT scan, should not be palpable on physical examination and should be considered normal size by imaging studies.
5. If the bone marrow was involved before treatment, the infiltrate must have cleared on repeated bone marrow biopsy. The biopsy sample on which this determination is made must be adequate (with a goal of  $> 20$  mm unilateral core). If a sample is indeterminate by morphology, it should be negative by IHC (if bone marrow was involved before therapy and a radiological CR was achieved, but with no bone marrow assessment after treatment, the response should be classified as a PR).
6. No new sites of disease are detected during assessment.

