### 3.4.3 Additional Information

#### 3.4.3.1 Response Assessments

Participants will be restaged at the following time points. Response assessments will be done by investigators. For additional details on response criteria, see Section [6.3](#).

- After cycle 1 (within 7 days prior to treatment on day 1 of cycle 2)
- After cycle 3 (within 7 days prior to treatment on day 1 of cycle 4)
- After cycle 6 (cycle 6 day 21 +/- 7 days)

**NOTE:** If a participant stops treatment for any reason other than disease progression before completion of 6 cycles, response assessments should continue as listed in Study Calendar ([Appendix D](#)).

**NOTE:** Restaging scans should only be performed based on involved sites of disease at baseline (e.g., patients with CNS disease only should undergo restaging MRI brain and PET brain while those with systemic disease should also undergo CT C/A/P and PET torso).

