### 6.3.3 Partial Response (PR)

For PR determination in participants with measurable disease, all the following criteria must be met:

1. A  $\geq 50\%$  decrease in the sum of the product of the diameters (SPD) of up to 6 of the largest dominant nodes or nodal masses.
2. No increase should be observed in the size of other nodes, liver, or spleen, meeting the criteria for PD.
3. Splenic and hepatic nodules must regress by  $\geq 50\%$  in the SPD or, for single nodules, in the GTD.
4. With the exception of splenic and hepatic nodules, other organs should not have any measurable disease.
5. Bone marrow assessment is not required for PR determination.
6. No new sites of disease should be observed.
7. At least 1 PET-positive site of disease (required for the CT+PET assessment of PR).

For PR determination in participants with evaluable disease that is not measurable, all the following criteria must be met:

1. A  $\geq 50\%$  decrease in the SUVmax from baseline PET scan.
2. Bone marrow assessment is not required for PR determination.
3. No new sites of disease should be observed.
4. At least 1 PET-positive site of disease (required for the CT+PET assessment of PR).

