#### 6.3.6 The Five-Point Deauville Scale (5-PS) for SCNSL

In addition to the CNS lymphoma working group criteria, the five-point Deauville scale (5-PS) has been validated for use at interim staging and at the end of treatment for systemic lymphomas

and was adopted as the preferred reporting method at the First International Workshop on PET in Lymphoma in Deauville, France (i.e., Deauville criteria), and in several international trials.

The 5-PS scores the most intense uptake in a site of initial disease:

1. if present, as follows: no uptake or no residual uptake (when used at interim)
2. slight uptake, but below blood pool (mediastinum)
3. uptake above mediastinal, but below or equal to uptake in the liver
4. uptake slightly to moderately higher than liver
5. markedly increased uptake or any new lesion (on response evaluation)

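### SCNSL complete response depends on a PET scale referenced only to mediastinum and liver, with no rule for brain sites, so CR with brain lesions may be under-recorded or scored inconsistently

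*Combined protocol and SAP*

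**What the plan says.** Section 6.3.2, Complete Response, is conjunctive: "For CR determination, all the following criteria must be met". Its third item is that the "FDG-PET scan must be negative (for the combined CT+PET assessment of CR"), and it fixes the cut-off on the five-point Deauville scale (5-PS), "with a score of 1-3 being considered PET negative and 4-5 considered PET positive".

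Section 6.3.6 defines the scale: "The 5-PS scores the most intense uptake in a site of initial disease". The highest level that still counts as negative is "uptake above mediastinal, but below or equal to uptake in the liver"; anything above liver is 4 or 5. Mediastinal blood pool and liver are the only reference tissues named. The same section says that the scale "has been validated for use at interim staging and at the end of treatment for systemic lymphomas".

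The rule reaches the brain. Section 3.4.3.1 says that "patients with CNS disease only should undergo restaging MRI brain and PET brain", and a footnote to the Appendix D calendar uses PET after cycle 6, or earlier when CR is suspected, to confirm CR.

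For PR in disease that can be evaluated but not measured, Section 6.3.3 asks for at least a 50% "decrease in the SUVmax from baseline PET scan". For PCNSL, Section 6.3.1 judges brain lesions on contrast enhancement, with steroid dose, eye examination and CSF cytology. It does not use PET.

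**The concern.** SCNSL can involve the brain, and in those participants the brain is a site of initial disease. A scale with liver as its ceiling works where healthy tissue takes up no more FDG than liver. If healthy brain takes up more, a lesion that has resolved completely leaves a site that still reads above liver. Read literally, that site is PET-positive and fails one of the required CR items. Nothing in Sections 6.3.2 to 6.3.6 names surrounding brain as a reference or makes an exception for physiological uptake.

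At stake is the CR rate, a secondary endpoint. Section 10.1 chooses CR as the informative response measure and treats PR as irrelevant because all such participants relapse. If a cleared lesion ends up as stable disease, ORR and duration of response are affected too.

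**Working it through.** **1. The plan's own figure.** The only design calculation is in Section 10.2: at least 7 successes in 10. Exact binomial: P(X ≥ 7 | 0.5) = (120 + 45 + 10 + 1)/1024 = 176/1024 = 0.1719, and P(X ≥ 7 | 0.8) = 0.8791. These reproduce the stated 17.2% and 87.9%. Success there means completing two cycles without stopping for toxicity, so PET scoring does not enter.

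**2. The scale applied literally.** Let r be uptake at the cleared brain site divided by liver uptake. The documents give no value, so r is an assumption.
- r = 0.8 or 1.0: score no higher than 3, PET-negative, CR possible.
- r = 1.1, 1.5, 2, 3 or 5: score 4 or 5, PET-positive, third CR item failed.

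The result turns only on whether r exceeds 1, not on its exact size.

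**3. Same brain result, two sets of criteria.** Take a brain lesion with no remaining enhancement, no steroids, normal eyes and negative CSF.
- PCNSL (Section 6.3.1): CR.
- SCNSL (Section 6.3.2): the items on disappearance of disease may be met, but the PET item must be met as well. With r above 1 on a literal reading, it is not.

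Section 10.4.3 reports the CR rate in PCNSL and SCNSL, and Section 10.4.7 plans no subgroup analyses.

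**4. Effect on the CR rate.** Assume 10 participants evaluable for response. Each misclassified CR changes the rate by 1/10, or 10 percentage points. Exact (Clopper-Pearson) 95% intervals:

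| Recorded CR | Rate | 95% CI |
|---|---|---|
| 6/10 | 60% | 26.2 to 87.8 |
| 5/10 | 50% | 18.7 to 81.3 |
| 4/10 | 40% | 12.2 to 73.8 |
| 3/10 | 30% | 6.7 to 65.2 |

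The number of SCNSL participants with brain lesions is not given and could be anything from 0 to 10.

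**5. PR.** Section 2.1.1.3 treats masses on MRI as measurable, so a brain mass falls under the measurable-disease rule in Section 6.3.3. That rule counts shrinkage only in nodes, liver and spleen, and allows no measurable disease in other organs. A brain mass that has shrunk by more than half but is still measurable therefore blocks PR.

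For non-measurable disease the rule uses raw SUVmax. If a lesion starts at t and normal brain reads b, the largest possible fall is 1 − b/t, which reaches 50% only when b is at most t/2. With assumed values (none in the documents): 1 − 7/15 = 53%, 1 − 9/15 = 40%, 1 − 11/15 = 27%, 1 − 7/10 = 30%. Full clearing can pass or fail depending on background.

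**The case against.** The strongest reply is that Section 6.3.6 already provides a way out. Score 1 covers a site with no remaining uptake, and a reader could put a lesion indistinguishable from surrounding brain there. That stands as an arguable reading. But the wording ties absence of residual uptake to interim use, while CR is confirmed chiefly after cycle 6, and brain at normal uptake is not a site without uptake. The text is therefore ambiguous at the time point that matters, and investigators read the response in an open-label study.

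A reader might go further and infer that SCNSL participants with brain disease can never be recorded as CR. The documents do not support that. They give no brain or liver uptake values, and the score 1 route is not closed. Nor does the point cover all SCNSL: Section 1.2.4 lists brain, eyes or CSF, and describes CNS involvement at diagnosis as usually leptomeningeal. The documents offer no basis for projecting a particular shortfall in the CR rate.

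Two further replies carry less weight. Section 6.3.6 presents the 5-PS as an addition to the CNS working group criteria, which might suggest that MRI also counts in SCNSL; but Section 6.3.1 limits those criteria to PCNSL, and an addition would not remove the PET item. Section 10.1 names Lugano for CR, and the cited sources might deal with physiological uptake. They cannot be consulted here, and Section 6.3.2 names a different set, the Revised Response Criteria, so the documents do not settle which governs.

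It is also fair that CR is a secondary, descriptive endpoint and that the intervals at n = 10 are wide.

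**Conclusion.** The concern holds as a defect in a secondary endpoint definition. The SCNSL rule makes CR depend on a scale with only mediastinum and liver as references, applies it to the brain, and has no MRI criterion for brain lesions. If normal brain uptake exceeds liver, CR in SCNSL participants with brain lesions may be under-recorded or may vary by reader. The same brain finding can be CR in PCNSL and not CR in SCNSL. Neither PR rule fits a brain lesion.

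The size is 10 percentage points per misclassified participant with 10 evaluable; the number at risk is unknown. PCNSL, SCNSL confined to eyes or CSF, and the primary endpoint with its 7-of-10 rule are not affected. The conclusion rests on one assumption from outside the documents, that the brain-to-liver uptake ratio is above 1.

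**What to change.** Amend Sections 6.3.2, 6.3.3 and 6.3.6 as follows.

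- Limit the mediastinum and liver 5-PS, and the raw SUVmax rule for PR, to disease sites outside the CNS.
- Judge CNS sites in SCNSL by the MRI, eye and CSF criteria already in Section 6.3.1. State that overall CR needs CR in both the CNS and systemic components, and how the unconfirmed CR category in that table counts towards the CR rate.
- If brain PET contributes to response, read it against surrounding normal brain.
- Reconcile the criteria named in Sections 6.3.2, 6.3.6 and 10.1, so that one governing set is identified for each disease group.

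The cost is protocol wording. Appendix D already schedules brain MRI after cycles 1, 3 and 6, and repeat CSF and eye assessments where baseline was positive, so the scans and readers stay the same. The one downside is that CNS sites in SCNSL would no longer use the published 5-PS reference.

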### 6.3.3 Partial Response (PR)

For PR determination in participants with measurable disease, all the following criteria must be met:

1. A  $\geq 50\%$  decrease in the sum of the product of the diameters (SPD) of up to 6 of the largest dominant nodes or nodal masses.
2. No increase should be observed in the size of other nodes, liver, or spleen, meeting the criteria for PD.
3. Splenic and hepatic nodules must regress by  $\geq 50\%$  in the SPD or, for single nodules, in the GTD.
4. With the exception of splenic and hepatic nodules, other organs should not have any measurable disease.
5. Bone marrow assessment is not required for PR determination.
6. No new sites of disease should be observed.
7. At least 1 PET-positive site of disease (required for the CT+PET assessment of PR).

For PR determination in participants with evaluable disease that is not measurable, all the following criteria must be met:

1. A  $\geq 50\%$  decrease in the SUVmax from baseline PET scan.
2. Bone marrow assessment is not required for PR determination.
3. No new sites of disease should be observed.
4. At least 1 PET-positive site of disease (required for the CT+PET assessment of PR).

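### Read literally, the SCNSL response rules score a halved, PET-positive brain mass as stable disease and leave unclear whether a CSF-only or small ocular relapse is progression

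*Combined protocol and SAP*

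**What the plan says.** Section 6.3 has two rulebooks. The CNS working group table in Section 6.3.1, with columns for brain imaging, steroid dose, eye and CSF, "will be used for participants on study with PCNSL". Its imaging criterion for PR is "50% decrease in enhancing tumor", and it lists both ocular and CSF recurrence under PD. For SCNSL, Section 6.3.2 says that the categories "are based on the Revised Response Criteria for Malignant Lymphoma", and the items that follow are systemic:

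- **CR (second Section 6.3.2).** Item 1 requires all detectable disease to be gone. Item 2 states: "All splenic and hepatic nodules and other extranodal disease must have disappeared". Item 3 adds: "A posttreatment residual mass of any size is permitted as long as it is PET-negative".
- **PR, measurable disease (Section 6.3.3).** All items must be met. Item 1 measures the summed product of diameters "of up to 6 of the largest dominant nodes or nodal masses". Item 4 reads: "With the exception of splenic and hepatic nodules, other organs should not have any measurable disease".
- **PR by SUVmax (Section 6.3.3).** This route opens with the words "For PR determination in participants with evaluable disease that is not measurable".
- **PD (Section 6.3.5).** The items cover new nodes, a new extranodal lesion over 1.0 cm, and 50% growth of nodes or other lesions. Item 5 asks for cytology only to confirm a new PET-negative CT lesion.

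Section 10.4.3 reports ORR, DOR and PFS over PCNSL and SCNSL, and Section 10.4.7 plans no subgroups. Section 10.1 labels the CR endpoint as Lugano, a name that Section 6.3 never uses; Section 10.3.2 sends classification to Section 6.3.

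**The concern.** Section 1.2.4 describes SCNSL as disease of the brain, eyes or CSF and includes isolated CNS relapse. The compartment that defines the cohort is thus the one that the SCNSL criteria handle least well. The same finding can be a response in a PCNSL participant and stable disease in an SCNSL participant, or progression in one and undefined in the other, and both feed a single estimate.

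The two gaps push in opposite directions. The PR gap lowers ORR. The PD gap, if the items are followed literally, lengthens PFS and DOR. They act on different endpoints, so one does not offset the other. Response is assessed by investigators in an open-label study (Sections 3.1 and 3.4.3.1), so where the rule is silent, the endpoint rests on individual judgement.

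**Working it through.** **Plan's own figures.** The plan gives no design figure for response. Its only operating characteristics (Section 10.2: 7 or more successes of 10) reproduce by exact binomial: 0.1719 at a true rate of 50% (stated 17.2%) and 0.8791 at 80% (stated 87.9%). Success there means completing two cycles without stopping for toxicity, so these figures do not depend on Section 6.3.

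**Step 1: a brain mass that halves.** Section 2.1.1.3 accepts masses measured on MRI, so a brain lesion can be measurable. Suppose that it goes from 3.0 x 3.0 cm to 2.0 x 2.0 cm and stays PET-positive.

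- Area: 9.0 to 4.0 cm²; decrease = 1 - 4.0/9.0 = 55.6%.
- Assumptions: tumor size is taken as the product of diameters, and 2.0 cm counts as measurable. The plan fixes neither for the brain.

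| Rule | Result |
|---|---|
| PCNSL PR, imaging column (6.3.1) | Met |
| SCNSL PR item 1 | Counts nodes only; in isolated CNS relapse there is no node to measure |
| SCNSL PR item 4 | Failed: measurable disease remains in an organ that is not exempted |
| SCNSL PR by SUVmax (6.3.3), and Section 10.3.3 | Not open: both are for disease that is not measurable |
| SCNSL CR item 3 | Failed: the mass is PET-positive |
| SCNSL PD | Not met: the lesion shrank |
| SCNSL SD (6.3.4) | Applies by default |

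If the residual mass were PET-negative, CR item 3 might admit it, although CR item 2 asks for extranodal disease to be gone. The clear loss from ORR is therefore confined to PET-positive residual masses.

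**Step 2: a relapse without a measurable lesion.**

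| Finding | PCNSL (6.3.1) | SCNSL (6.3.5) |
|---|---|---|
| CSF turns positive, imaging unchanged | Listed under PD | No item applies |
| Ocular relapse, no lesion over 1.0 cm | Listed under PD | No item applies |
| New ocular or brain lesion over 1.0 cm | PD | PD (item 2) |

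Section 3.4.3.2 requires CSF testing at suspected progression, and an eye examination if the eye was involved at baseline. The data would exist, but no SCNSL progression item uses them.

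**Step 3: size.** Taking the 10 evaluable participants of Section 10.2 as the ORR denominator, one reclassification moves ORR by 1/10 = 10.0 points. With exact (Clopper-Pearson) 95% intervals:

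- 6/10 = 60%, interval 26.2% to 87.8%
- 5/10 = 50%, interval 18.7% to 81.3%

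The 10 points are simply 1/n. The documents give neither the PCNSL/SCNSL split nor a rate of measurable residual brain disease, so the number of such participants cannot be estimated and may be zero.

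**The case against.** The best counter-argument is that CNS findings were meant to count. Section 6.3.6 is headed for SCNSL and opens by mentioning the CNS working group criteria; Appendix D repeats CSF and eye assessments in any participant positive at baseline; and Section 3.4.3.2 asks for CSF testing without distinguishing the two diseases. This supports the view that the authors intended it. It does not supply the rule: the remark in Section 6.3.6 introduces the Deauville scale and assigns nothing, while Section 6.3.1 limits its scope to PCNSL.

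It can also be said that the plan discounts PR (Section 10.1 calls it not relevant because all will relapse), that response is secondary, and that ORR, DOR and PFS carry no decision threshold. All of this stands and limits the weight of the point.

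A reader might infer more than the documents support:

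- *That the systemic criteria ignore the brain.* They do not. CR items 1 and 2 and PD items 2 and 3 reach brain lesions.
- *That a CSF-only relapse certainly does not end PFS or DOR.* Sections 6.3.8 and 6.3.9 speak of recurrence or relapse without citing Section 6.3.5, and documented positive cytology could be read as such. The position is unclear rather than settled.
- *That such a relapse after a PET-negative CR has no category.* SD item 1 is a catch-all, and item 2 is tied to the combined CT and PET assessment.
- *That detection waits for the next scheduled follow-up scan.* Section 3.4.3.2 requires MRI, CT and CSF testing at suspected progression.
- *That the CR rate is scored by the wrong system.* Section 10.3.2 already points to Section 6.3, so Lugano is a label problem only.

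**Conclusion.** The point holds for the secondary endpoints ORR, DOR and PFS. As written, an SCNSL brain response of 50% or more that stays measurable and PET-positive is stable disease, and the plan does not say whether a CSF-only or small ocular SCNSL relapse is an event. Each participant reclassified for response shifts ORR by 10 points at n=10; the number affected is unknown. The PR conclusion assumes a literal reading of PR item 4 and that the residual brain lesion counts as measurable. The PD conclusion is that the rule is missing, not that events will necessarily be lost. The primary endpoint, sample size and OS are unaffected. It is worth fixing because the correction is cheap and uses data already scheduled.

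**What to change.** Amend Sections 6.3.2 to 6.3.5 as follows:

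1. Score the CNS compartment of SCNSL by the MRI, CSF, eye and steroid criteria of Section 6.3.1, and the systemic compartment by the existing criteria.
2. State that any CNS finding that is not CR, CRu, PR or PD is SD. The Section 6.3.1 table has no SD row, so a ranking needs this.
3. State that CRu counts as a response in ORR for both PCNSL and SCNSL, and say whether it counts in the CR rate. Section 10.1 defines ORR as CR plus PR and leaves CRu unplaced.
4. Define overall response as the worst of the compartments involved at baseline, in the order CR, CRu, PR, SD, PD.
5. State that new disease or PD in either compartment, including positive CSF or new or recurrent ocular disease, is PD for PFS and DOR.

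As a tidy-up, replace the Lugano label in Section 10.1 with a reference to Section 6.3.

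The cost is a slightly longer response section. No new procedures are needed: brain MRI, CSF, eye and concomitant medication (steroid) data are already scheduled in Appendix D, and Section 3.4.3.2 covers the work-up at suspected progression.
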